8.7.5. Efficacy Analyses

Summary statistics will be calculated for each of the efficacy endpoints. For categorical endpoints, numbers and percentages, and 95% confidence intervals will be calculated. For continuous variables, numbers, means, medians, minimum, maximum, standard deviations, and standard error of means, and 95% confidence intervals will be calculated. Geometric means will be calculated for UPCR and urinary MCP-1:creatinine, and other data that are not normally distributed.

Results will be presented by treatment group. Results will be presented by stratum for C3GN vs. DDD and renal transplant vs. no renal transplant. Data will also be presented by geographic distribution (North America vs. Rest of World), sex, age group (including a separate analysis in 12-17 year old patients), race, and ethnicity for at least the primary endpoint.

The overall efficacy hypothesis in this study is that avacopan treatment will be effective in treatment of patients with C3G based on improvement in renal histology (C3G histologic index of activity).

The primary efficacy endpoint is the percent change from baseline to Week 26 in the C3G Histologic Index for disease activity.

- The null hypothesis (H_0) is that the avacopan group is not different from the placebo group when comparing the percent change from baseline to Week 26 in the C3G Histologic Index for disease activity.
- The alternative hypothesis (H_1) is that the avacopan group is superior to the placebo group when comparing the percent change from baseline to Week 26 in the C3G Histologic Index for disease activity.

Avacopan and placebo groups will be compared by ANCOVA with treatment group as factor and baseline C3G Histologic Index for disease activity as covariate. A point estimate and corresponding 95% confidence interval will be estimated for the treatment main effect. The heterogeneity of the treatment effect across disease diagnoses and renal transplant strata will be investigated through subgroup analyses. If data are not normally distributed, in addition to the ANCOVA for the percent change in C3G Histologic Index for disease activity and chronicity,

the Cochran-Mantel-Haenszel (CMH) test will be applied to the percent change results and ANCOVA will be applied to the change in C3G Histologic Index disease activity and chronicity scores.

The treatment effect based on the baseline complement profile of patients will also be investigated.

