5.2 Primary Efficacy Analysis

The primary efficacy endpoint is the percent change from baseline to Week 26 in the C3G Histologic Index for disease activity. The C3G Histologic Index for disease activity can assume a score from 0-21. See Section 2.3.4 for further details on the calculation of C3G Histologic Index for disease activity.

Statistical Hypothesis Testing and Procedure

• The null hypothesis (H0) is that the avacopan group is not different from the placebo group when comparing the percent change from baseline to Week 26 in the C3G Histologic Index for disease activity.

• The alternative hypothesis (H1) is that the avacopan group is different from the placebo group when comparing the percent change from baseline to Week 26 in the C3G Histologic Index for disease activity.

Numbers, means, median, standard deviation, standard error of means, minimum and maximum will be presented by treatment group and study visit. Avacopan and placebo groups will be compared by Analysis of Covariance (ANCOVA) with treatment group as factor and baseline C3G Histologic Index for disease activity as a covariate. The LS mean estimate and corresponding 95% confidence interval (CI) will be estimated for the treatment main effect. The heterogeneity of the treatment effect across disease diagnoses and renal transplant strata may be investigated through subgroup analyses.

As there are no data available to access the possibility of non-normality distribution of percent change or change from baseline, normality distribution tests will be performed for both percent change and change from baseline. It is possible that the normality test would not hold for percent change from baseline or change from baseline or both. In this case, the following is the analysis procedures for the primary efficacy endpoint.

• If the test for normality fails for percent change from baseline at α level of 0.10 but not change from baseline, change from baseline will be used as the primary endpoint;

• If the test for normality fails for both percent change and change from baseline at α level of 0.10, percent change from baseline will be used as the primary endpoint, but non-parametric methodology will be used for the primary endpoint analysis. The van Elteren's test will be applied to test the percent change from baseline endpoint.

The treatment effect based on the baseline complement profile of subjects may also be investigated.

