The SAS code to generate the Analysis of Covariance will be similar to the following:

See Appendix 12.3 for the SAS code to perform van Elteren's test to compare the two treatment groups using the imputed datasets.

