5.2.1 Primary Analysis

The primary analysis will be based on the ITT population in the elevated C5b-9 stratum (>244 ng/ml). The primary analysis is based on percent change from baseline to Week 26 during the double-blind treatment period and will be analyzed using the ANCOVA analysis methods described above. Both percent change from baseline and change from baseline will be summarized and analyzed with percent change from baseline being the primary efficacy endpoint.

Multiple Imputation Method

Missing data used to calculate the primary endpoint will be handled using the Missing at Random (MAR) multiple imputation method. The multiple imputation procedure will be conducted in two parts using SAS[®] PROC MI and PROC MIANALYZE.

The primary analysis will be carried out by imputing missing data for the 7 lesions that comprise the Histological Index for Disease Activity. The multiple imputation model will include the two stratification factors (disease type [C3G or DDD] and kidney transplant status [Y/N]), treatment group, in addition to values at each visit from baseline through week 26. For each lesion component, 100 'complete' datasets will be generated using SAS[®] PROC MI. The seeds for the imputation will be specified as '12061', '36102', '94218', '20949', '60137', '80230' and '59137', for imputation of 7 lesion activity scores, respectively. Imputed individual lesion component scores will then be classified into scale scores (e.g., leukocyte infiltration % involvement = 29% would translate to a scale score of 2). The 'complete' datasets for the individual components of the lesion activity scores will be merged by imputation number and summed to calculate the Histological Index for Disease Activity and creation of 100 'complete' datasets for evaluation of activity scores.

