10 CHANGES FROM PROTOCOL-SPECIFIED STATISTICAL ANALYSES

- The protocol specified 3 analysis populations for the study including the primary elevated C5b-9 population, the non-elevated C5b-9 population and the combined population. Due to the small sample size in the non-elevated C5b-9 stratum, the primary elevated C5b-9 population will remain as the primary population and the two strata combined (including both elevated and non-elevated C5b-9) will be considered the secondary population for analysis. Data from the non-elevated C5b-9 stratum will only be summarized.
- ITT population definition change to exclude subjects who had baseline C3G Histologic Index of activity score of 0.
- Secondary efficacy endpoint order rearranged.

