/* Note: In the code above, remove minimum and maximum when imputed value is out of range; replace percentage <0 to be 0 and replace percentage >100 to be 100 for imputed values $^{*/}$

If imputation at Week 52 is explored, code similar to the following will be used.

```
/* Imputation at Week 52 */
Proc MI Data= mum_mi26 Seed= Seedno nimpute= 1
    minimum= . . . 0
    maximum= . . . 100
    Out= mum_mi52;
    by _imputation_ TRT01PN;
    class DISTYPE RENTRANS;
    var DISTYPE RENTRANS BL W26 W52;
    monotone reg(W52/details) ;
Run;
/* Note: In the code above, if the model is not able to be fit, remove Renal
Transplant Status (RENTRANS) */
```

The 1 classification variable in disease activity and 2 classification variables in disease chronicity will be imputed using SAS code below.

```
/* Imputation at Week 26 */
Proc MI Data= cat_org Seed= Seedno nimpute=100
    out= cat_mi26;
    by TRT01PN;
    class DISTYPE RENTRANS BL;
    war DISTYPE RENTRANS BL;
    monotone logistic(W26= DISTYPE RENTRANS BL/ Details Likelihood=AUGMENT) ;
run;
proc sort data= cat_mi26;
    by _imputation_ TRT01PN;
run;
```

If imputation at Week 52 is explored, code similar to the following will be used.

The Summary Statistics, such as Mean and Standard Errors for Imputed dataset are obtained as follows:

```
Note:
    EFFI = Imputed efficacy analysis dataset
    AVAL = Variable analyzed
    Imputation = Imputed number
    TRT01PN = Treatment Group (Placebo/Avacopan)
*** Proc Univariate to generate sample means and standard errors for the variables in
each imputed data set
Proc Univariate Data= EFFI;
     By _Imputation ;
     Class TRT01PN;
     Var AVAL;
     Output Out= SumStat MI
          Mean= AVAL
          Stderr= SAVAL;
Run;
Proc sort data= SumStat MI; By TRT01PN; Run;
*** Proc MIANALYZE;
PROC MIANALYZE DATA = SumStatMI;
     By TRT01PN;
     Modeleffects AVAL;
     Stderr SAVAL;
     ODS Output
          ParameterEstimates = SumStat Mian;
RUN;
```

Note: If variables not requested imputation, the above procedure won't be appropriate. Using PROC MEANS to summary one single imputation to get summary statistics.

The ANCOVA analysis will be carried out using the following:

```
Note:
     EFFI = Imputed efficacy analysis dataset
     Response = CHG/PCHG
     CHG = Change from baseline in C3G Disease Activity or Chronicity
     PCHG = Percent change from baseline in C3G Disease Activity or Chronicity
     Base = Baseline value

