     TRT01PN = Treatment Group (Placebo/Avacopan)
*** Perform ANCOVA;
PROC MIXED DATA= EFFI;
     By Imputation ;
     Class TRT01AN(ref='1');
     Model Response = TRT01AN Base / solution cl ddfm = KR
                   residual OUTP = ano_res ;  * studentized residual ;
     Lsmeans TRT01AN / Alpha=0.05 cl diff ;
     ODS Output LSMEANS = ano lsm
                    Diffs = ano diff;
RUN;
*** Combine result;
PROC MIANALYZE DATA = ano lsm;
     By TRT01AN;
     Modeleffects Estimate;
     Stderr;
     ODS Output
           ParameterEstimates = miana_lsm;
RUN;
PROC MIANALYZE DATA = ano diff;
     By TRT01AN;
     Modeleffects Estimate;
     Stderr;
     ODS Output
           ParameterEstimates = miana diff;
RUN;
*** Normality Test;
PROC UNIVARIATE DATA = ano_res Normaltest;
     Class Imputation ;
     Var StudentResid;
     ODS Output
           TestsForNormality = res SW (Where=(Test="Shapiro-Wilk"));
Run;
*** Select the minimum P-value from Shapiro-Wilk test among all imputation;
```

For the primary analysis of change from baseline to Week 26 in C3G Histological Index of Disease Activity and Disease Chronicity, the normality test is performed on the imputed data using the Shapiro-Wilk test where the lowest p-value is selected. If the p-value is < 0.01, normality is rejected, van Elteren's test is used for the treatment comparison. The steps to carry out the analysis are detailed below.

```
Note:
     EFFI = Efficacy Analysis Dataset with multiple imputation
     Response = categorical variable of interest in analysis
     DISTYPE = Disease Type (C3GN or DDD)
     RENTRANS = Renal Transplant Status (Y/N)
     TRT01PN = Treatment Group (Placebo/Avacopan)
*** Van Elteren's Test by each Imputation;
Proc Freq Data= EFFI;
     By Imputation ;
     Table DISTYPE*RENTRANS*TRT01PN*Response / CMH Scores= modridit;
     Ods Output
          CMH= cmh RMS (Where=(AltHypothesis="Row Mean Scores Differ"));
Run;
*** Apply Wilson-Hilferty transformation to the CMH statistic and standardize the
resulting normal variable;
DATA cmh wh;
     SET cmh RMS;
     cmh value wh = ((VALUE/DF)**(1/3) - (1-2/(9*DF)))/SQRT(2/(9*DF));
     cmh sterr wh = 1.0;
RUN;
*** Proc MIANALYZE;
PROC MIANALYZE DATA = cmh wh;
     Modeleffects cmh value wh;
     Stderr cmh_sterr_wh;
     ODS Output
           ParameterEstimates = cmh miana;
RUN;
```

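### SAP Section 5.2 and Appendix 12.3 give two different normality rules for choosing the primary Week 26 analysis, and nothing says which governs

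*SAP*

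**What the plan says.** **SAP Section 5.2** pre-tests normality on two scales. The first branch reads "If the test for normality fails for percent change from baseline at α level of 0.10 but not change from baseline"; the consequence is that absolute change replaces percent change as the primary endpoint. If both scales fail at 0.10, percent change stays primary but is tested by van Elteren's test.

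**SAP Appendix 12.3** states that "the normality test is performed on the imputed data using the Shapiro-Wilk test where the lowest p-value is selected". It continues: "If the p-value is < 0.01, normality is rejected, van Elteren's test is used for the treatment comparison". The code applies the test to studentized ANCOVA residuals. The appendix neither repeats nor excludes the endpoint switch. Its sentence speaks only of change from baseline, while its code note has "Response = CHG/PCHG".

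**Links between the two.** Section 5.2 sends the reader to the appendix for code: "See Appendix 12.3 for the SAS code to perform van Elteren's test to compare the two treatment groups using the imputed datasets". Section 5.2.1 sends the reader there for further detail, and itself says "Both percent change from baseline and change from baseline will be summarized and analyzed with percent change from baseline being the primary efficacy endpoint", without repeating the condition from 5.2. The SAP Introduction ranks the SAP above the protocol, but not one part of the SAP above another.

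**Protocol Section 8.7.5** adds analyses rather than replacing any: "If data are not normally distributed, in addition to the ANCOVA for the percent change in C3G Histologic Index for disease activity", a CMH test on percent change and an ANCOVA on change are to be run. SAP Section 10 lists three changes from the protocol: the analysis populations by C5b-9 stratum, the ITT definition ("ITT population definition change to exclude subjects who had baseline C3G Histologic Index of activity score of 0") and the order of the secondary endpoints. The move from adding to replacing is not among them.

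**The concern.** Under SAP Section 3.1 the primary test in the elevated C5b-9 stratum carries the trial's main claim. It also opens the combined-strata test and the chronicity test in the same stratum. A confirmatory test of that kind must be fixed before unblinding. Here two analysts who each follow the SAP faithfully could report a different primary endpoint, estimate and p-value, and the choice between them could be made with the results in view.

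Two lesser points come with it. Taking the lowest of 100 p-values cannot hold a 1% level once data are imputed, and 5.2 does not say how its own 0.10 test is combined over imputations. Also, the printed van Elteren pooling code, if its default p-value is reported, gives p-values that are too large.

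**Working it through.** **1. The plan's own figure.** SAP Section 9 and Protocol Section 8.8 give a difference of 35, SD 34, 90% power and two-sided 0.05. The normal approximation gives n = 2(1.96 + 1.2816)² × 34²/35² = 19.8, so 20 per arm. By the t distribution, 21 per arm gives 90.2% power and 22 gives 91.5%. The stated 22 reproduces and is used below.

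**2. The rules side by side.** The same p-values are fed to both rules. Appendix 12.3 is read on percent change, without a switch.

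| p, percent change | p, change | Section 5.2 | Appendix 12.3 |
|---|---|---|---|
| ≥0.10 | any | ANCOVA, percent change | ANCOVA, percent change |
| 0.01 to <0.10 | ≥0.10 | ANCOVA, change | ANCOVA, percent change |
| 0.01 to <0.10 | <0.10 | van Elteren | ANCOVA, percent change |
| <0.01 | ≥0.10 | ANCOVA, change | van Elteren |
| <0.01 | <0.10 | van Elteren | van Elteren |

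The rules disagree in three of the five rows. This follows from the text alone.

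**3. How often it matters.** From the documents: 22 per arm, effect -35%, SD 34%, integer scores 0-21. Assumed, because the documents give no baseline scores: the baseline mean/SD pairs below, and no missing data. There were 5,000 runs per setting, with Shapiro-Wilk on studentized ANCOVA residuals and a single-stratum rank test with the correct p-value.

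| Baseline mean/SD | 6/3 | 8/3 | 10/3 | 10/2 |
|---|---|---|---|---|
| Percent change normal: different primary analysis | 12.2% | 8.8% | 9.4% | 8.7% |
| Percent change normal: significance differs | 1.0% | 0.6% | 0.4% | 0.2% |
| Absolute change normal: different primary analysis | 54.4% | 36.0% | 23.0% | 12.8% |
| Absolute change normal: significance differs | 6.4% | 2.5% | 1.5% | 0.3% |

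- If the appendix's silence is read as keeping the 5.2 switch, so that only the threshold differs, the analyses differ in 9-12% (percent normal) or 13-25% (absolute normal), and significance in 0.2-1.1% or 0.2-3.4%.
- Type I error is 4.7-6.0% under 5.2 and 4.5-6.0% under 12.3. Choosing the more favourable rule after unblinding gives 4.8-5.2% (percent normal) or 5.0-7.4% (absolute normal).
- A separate simulation with baseline 8/3.5 gave different analyses in about 10-11% and 48-54% with nothing missing. With 10% missing, 100 imputations and the lowest p used for both rules, it gave 42-53%.

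**4. Lowest p over imputations.** Scores were truly normal and imputed by regression within arm, with 1,000 runs. With an assumed 2, 4 or 6 missing values, the lowest p falls below 0.01 in 11%, 22% and 30% of trials. A single test on observed cases does so in 0.4-1.0%. With seven lesions imputed, categorised and summed (assumed distributions, not normal; 600 runs), the figures are 55%, 64% and 70%, against 36%, 34% and 32% for observed cases.

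**5. Van Elteren pooling code.** With one degree of freedom the printed transformation is z = (v^(1/3) - 7/9)/√(2/9). Only large positive z is evidence against the null. If a two-sided p around zero is reported, significance needs z = 1.96, so v = (0.7778 + 1.96 × 0.4714)³ = 4.93 instead of 3.84. The real level is 0.026. A true p of 0.05 prints as 0.094, and 0.04 as 0.075. In 4,000 runs per setting with one stratum, the power loss was 6-7 points with normal data and 2-4 points with skewed data.

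**The case against.** The strongest reply is that Appendix 12.3 concerns only the analysis of the change scale. Its sentence names change from baseline, and Section 5.2.1 has both scales analysed. On that reading there is no conflict: 5.2 makes change primary only if it passes at 0.10, and the same p-value cannot then be below 0.01. The reading is possible but weak. The code note covers both scales, and the appendix presents itself as the method for the missing Week 26 activity index. A second reply is that 12.3 merely supplies the working detail of 5.2. That would explain Shapiro-Wilk and the lowest p, but it cannot turn 0.10 into 0.01 or settle the switch.

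It can also be said that the SAP Introduction requires primary-analysis revisions before lock or snapshot. That limits new revisions, not the choice between two rules already printed.

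Several objections to size do stand. Verdicts seldom change, and the largest figures come from one assumed corner: baseline 6/3 with absolute change normal. The lesion-level figures rest on assumed distributions in which observed cases already reject often, so only the score-level 11-30% shows inflation over the nominal 1%. The pooling point applies only if the fallback is used and the default p-value reported. Some code is missing from the public text, so a later p-value step may exist. The 6-7 point power loss is for normal data, where the fallback would seldom be triggered.

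**Conclusion.** The concern holds: the primary analysis is contradictory as written and must be fixed before unblinding. The contradiction is textual and needs no assumption. Its practical size does depend on assumed baseline scores. If the design scale (percent change) is the normal one, the primary analysis differs in roughly one trial in ten and the verdict in at most 1%. If absolute change is normal, the analysis can differ in up to about half of trials and the verdict in up to 6.4%. Neither rule by itself materially inflates type I error. The defect is that the test behind the primary claim and its gates is not uniquely determined. The unlisted departure from the protocol is a documentation gap that belongs to the same correction. The pooling-code point is conditional and conservative: it costs power only.

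**What to change.** Before database lock, print one identical rule in Sections 5.2, 5.2.1 and Appendix 12.3. The simplest, and closest to Protocol Section 8.7.5, is ANCOVA on percent change as the fixed primary analysis, with ANCOVA on change and van Elteren's test on percent change as named sensitivity analyses.

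If a pre-test is kept, use one threshold, apply it once to observed-case residuals, state the outcome for every combination of the two scales, and list the switch in Section 10.

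In the van Elteren code, pool the signed standardised rank statistic with a two-sided p-value. Alternatively, take the upper-tail p of the pooled transformed score (critical v = 3.75, level about 0.053, slightly liberal). When nothing is imputed, report the CMH p-value directly.

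The cost is SAP wording and a few lines of code, with no extra patients or data. Dropping the pre-test loses some efficiency if data are strongly skewed or absolute change is the normal scale. In the worst assumed setting (baseline 6/3), power is 0.77, against 0.85 under the 5.2 rule and 0.82 under the 12.3 rule. The named sensitivity analyses would reveal that situation.

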5.2.1 Primary Analysis

The primary analysis will be based on the ITT population in the elevated C5b-9 stratum (>244 ng/ml). The primary analysis is based on percent change from baseline to Week 26 during the double-blind treatment period and will be analyzed using the ANCOVA analysis methods described above. Both percent change from baseline and change from baseline will be summarized and analyzed with percent change from baseline being the primary efficacy endpoint.

Multiple Imputation Method

Missing data used to calculate the primary endpoint will be handled using the Missing at Random (MAR) multiple imputation method. The multiple imputation procedure will be conducted in two parts using SAS[®] PROC MI and PROC MIANALYZE.

The primary analysis will be carried out by imputing missing data for the 7 lesions that comprise the Histological Index for Disease Activity. The multiple imputation model will include the two stratification factors (disease type [C3G or DDD] and kidney transplant status [Y/N]), treatment group, in addition to values at each visit from baseline through week 26. For each lesion component, 100 'complete' datasets will be generated using SAS[®] PROC MI. The seeds for the imputation will be specified as '12061', '36102', '94218', '20949', '60137', '80230' and '59137', for imputation of 7 lesion activity scores, respectively. Imputed individual lesion component scores will then be classified into scale scores (e.g., leukocyte infiltration % involvement = 29% would translate to a scale score of 2). The 'complete' datasets for the individual components of the lesion activity scores will be merged by imputation number and summed to calculate the Histological Index for Disease Activity and creation of 100 'complete' datasets for evaluation of activity scores.

For the subjects with missing data, continuous results of mesangial hypercellularity, endocapillary hypercellularity/proliferation, membranoproliferative morphology, leukocyte infiltration, crescent formation, fibrinoid necrosis will be imputed first and then their categorical results will be calculated in order to calculate Histological Index for Disease Activity. The results from the 100 fitted models will be combined using SAS[®] PROC MIANALYZE. The estimate of the treatment difference and standard error from the analysis will be analyzed by PROC MIANALYZE to obtain the overall estimate of treatment difference, as well as the confidence interval and p-value for the hypothesis testing.

See Appendix 12.3 for additional details.

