5.2.4 Completer Analysis

A completer analysis will also be carried out requiring subjects in ITT to have valid C3G Histologic Index for disease activity scores at Baseline and Week 26. The primary analysis is based on percent change from baseline to Week 26 during the double-blind treatment period and will be analyzed using the ANCOVA analysis methods described above. The primary analysis will be based on the in the elevated C5b-9 stratum (>244 ng/ml). The same analysis will also be carried out for the combined C5b-9 strata (subjects with elevated C5b-9 blood levels and non-elevated C5b-9 blood levels). This analysis will be repeated for the change from baseline also.

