5.2.5 Individual Components of C3G Histological Index Activity

Change from baseline in individual components of the C3G Histological Index Activities indices will also be summarized over time based on actual and imputed data.

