Multiple imputation will be used to impute missing data and will be implemented using SAS® PROC MI: Missing data may be the result of missing lesion components for calculation of C3G Histological Index of Disease Activity or Disease Chronicity or due to subjects discontinuing the study prior to Week 26 or Week 52. Missing at random (MAR) will be assumed. The primary analysis will be carried out by imputing missing data for the 7 lesions that comprise the Histological Index for Disease Activity and separately for the 4 lesions that comprise the Histological Index for Disease Chronicity. The multiple imputation model will include the two stratification factors (disease type [C3G or DDD] and kidney transplant status [Y/N]), treatment group, in addition values at each visit from baseline through week 26. If the model fails to converge, exclusion of stratification factors may be considered.

For each lesion component, 100 'complete' datasets will be generated using SAS® PROC MI. Imputed individual lesion component scores will then be classified into scale scores (e.g.,

leukocyte infiltration % involvement = 29% would translate to a scale score of 2). The 'complete' datasets for the individual components specific to disease activity and disease chronicity separately, will be merged by imputation number and summed to calculate the Histological Index for Disease Activity and Disease Chronicity and creation of 100 'complete' datasets for evaluation of activity and chronicity scores.

The results from the 100 fitted models will be combined using SAS® PROC MIANALYZE. The estimate of the treatment difference and standard error from the analysis will be analyzed by PROC MIANALYZE to obtain the overall estimate of treatment difference, as well as the confidence interval and p-value for the hypothesis testing. This will be done separately for Histological Index for Disease Activity and Histological Index for Disease Chronicity

The steps to carry out the primary multiple imputation and analysis are described below:

The 6 lesions in disease activity and 2 lesions in disease chronicity with continuous results will be imputed using SAS code below.

```
/* Imputation at Week 26 */
Proc MI Data= num_org Seed= Seedno nimpute= 100
    minimum= . . 0
    maximum= . . 100
    Out= mum_mi26;
    by TRT01PN;
    class DISTYPE RENTRANS;
    var DISTYPE RENTRANS BL W26;
    monotone reg(W26/details) ;
Run;
```

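### Imputing the seven lesions of a missing biopsy in separate runs understates the primary standard error if lesions are positively correlated, and the pooling calls omit the small-sample degrees of freedom

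*SAP*

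**What the plan says.** SAP 5.2.1 handles missing Week 26 histology by multiple imputation under missing at random. Each lesion gets 100 completed datasets from its own PROC MI run, with seven different seeds listed for the seven lesions. The "components of the lesion activity scores will be merged by imputation number and summed to calculate the Histological Index for Disease Activity".

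The code in Appendix 12.3 shows what each run conditions on: "var DISTYPE RENTRANS BL W26", run by treatment arm. BL is the baseline of the lesion being imputed, and no other lesion enters. The fallback is: "If the model fails to converge, exclusion of stratification factors may be considered".

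Within each completed dataset the ANCOVA requests small-sample degrees of freedom: "Model Response = TRT01AN Base / solution cl ddfm = KR". The treatment difference is then pooled by "PROC MIANALYZE DATA = ano diff", followed only by BY, MODELEFFECTS, STDERR and ODS OUTPUT. No pooling call shown carries EDF=.

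SAP 5.3.3 repeats the lesion-by-lesion design for the four chronicity lesions. The pattern-mixture sensitivity analysis also imputes one parameter at a time.

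**The concern.** Draw 17 for crescents and draw 17 for leukocyte infiltration come from unrelated runs, so merging on imputation number makes the lesions of one missing biopsy independent given each lesion's own baseline, disease type, transplant status and arm. Lesions read on the same tissue may well share residual variation, although the documents do not say so. If they do, the imputed totals are too alike, and both the within- and between-imputation variances shrink.

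Without EDF=, Rubin's degrees of freedom run into the thousands and the test uses a critical value of about 1.96, although the complete-data ANCOVA has only about 41 error df.

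The affected analysis is the primary test in the elevated C5b-9 stratum, which gates the combined-strata test (SAP 3.1). The effect is larger on the raw change scale. That scale matters because, under SAP 5.2, if normality fails for percent change "but not change from baseline, change from baseline will be used as the primary endpoint". The pattern-mixture analysis shares the design, so it would not reveal the problem.

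**Working it through.** **Inputs from the documents.** Two-sided α 0.05 (SAP 3.1); 22 per arm, difference −35%, SD 34%, power 90% (SAP 9); seven lesions scored 0–3 and summed to 0–21 (SAP 2.3.4); 100 imputations (SAP 5.2.1); ANCOVA with treatment and baseline, so 44 − 3 = 41 error df at the planned size.

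**Assumed, not in the documents.** The number of wholly missing Week 26 biopsies and the residual correlation ρ between lesions; both are ranged below.

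**The plan's own figure.** With difference 35 and SD 34, the normal formula gives 20 per arm and the t-test 21 (power 0.902). At 22 per arm the t-test power is 0.915. The planned size reproduces.

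**Variance of an imputed total.** For seven lesions of equal residual variance s², the sum has variance 7s²(1 + 6ρ). Separate draws give 7s², a share of 1/(1 + 6ρ): 1/2.8 = 36% at ρ = 0.3, 1/4 = 25% at ρ = 0.5, 100% at ρ = 0.

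**Effect on the pooled SE.** With missing share f, no covariates and many imputations:

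(SE as specified / correct SE)² = (1 − f)² + f(2 − f)/(1 + 6ρ)

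Example, f = 0.10 and ρ = 0.3: 0.81 + 0.19/2.8 = 0.878; square root 0.94.

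| Missing share | ρ = 0 | ρ = 0.3 | ρ = 0.5 |
|---|---|---|---|
| 5% | 1.00 | 0.97 | 0.96 |
| 10% | 1.00 | 0.94 | 0.93 |
| 20% | 1.00 | 0.88 | 0.85 |

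**Degrees of freedom.** Rubin df = 99(1 + 1/r)². At f = 0.10, r = 1.01 × 0.1/0.9 = 0.112, so df is about 9,700 and the critical value 1.960. Barnard–Rubin df with EDF = 41 is about 35, critical value 2.030. The interval is therefore 1 − 1.960/2.030 = 3.4% too narrow. Even with nothing missing, a 1.96 cut-off on 41 df has true size 0.0568.

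**Simulation A.** 4,000 null trials per setting, 22 per arm, 100 imputations, baseline to Week 26 correlation 0.5 (assumed), zero baselines excluded. Lesion percentages were imputed by arm on own baseline and disease type, limited to 0–100, categorised on the SAP scales and summed. Monte Carlo error is about 0.004. Simplifications: transplant status was left out, and lesions that the SAP imputes by logistic models were treated as continuous. The simulated SD of percent change was about 27% (ρ = 0.3) to 35% (ρ = 0.5).

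Type I error for percent change, as written:

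| ρ | 1 missing per arm | 2 | 4 |
|---|---|---|---|
| −0.1 | 0.047 | 0.041 | 0.027 |
| 0 | 0.056 | 0.048 | 0.042 |
| 0.3 | 0.064 | 0.059 | 0.064 |
| 0.5 | 0.056 | 0.055 | 0.069 |

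Ranges over ρ = 0.3–0.5 and 1, 2 or 4 missing per arm:

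| Endpoint | As written | EDF alone | Total imputed + EDF |
|---|---|---|---|
| Activity, percent change | 0.055–0.069 | 0.047–0.058 | 0.035–0.048 |
| Activity, change | 0.062–0.085 | 0.055–0.076 | 0.034–0.053 |
| Chronicity, change | 0.053–0.068 | 0.047–0.057 | 0.040–0.049 |

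The completer analysis of percent change gave 0.043–0.053. Relative to imputing the total, the lesion-by-lesion SE was smaller by 3–4% (1 missing), 6–8% (2) and 12–15% (4). For example, at ρ = 0.3 with 4 missing, mean SEs were 8.18 and 9.31, ratio 0.88. Relative to the true sampling SD it was 0.95–1.00 for percent change and 0.90–0.97 for change.

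**Simulation B.** Percent change, separately coded with transplant status in the imputation model, comparing separate runs with joint draws of all lesions. At ρ = 0.3–0.5, size as written was 0.056–0.066 (2 of 22 missing per arm), 0.077–0.079 (4) and 0.071–0.084 (6). With 0–3 scores it was 0.062–0.069 in the settings completed (2 missing, and 4 missing at ρ = 0.3). Joint draws with EDF = 41 gave 0.026–0.048 on the uncategorised scale. At ρ = 0 separate runs did not understate the SE (ratio to true SD 1.02–1.14).

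**The case against.** The strongest reply is that, for percent change, the lesion point hardly moves the test. With one missing biopsy per arm, size as written is 0.056 at both ρ = 0 and ρ = 0.5, which is the 0.0568 expected from the missing EDF. With EDF alone, size is at most 0.008 above nominal, whereas imputing the total can fall 0.015 below it. This stands: on that scale EDF does most of the work, and imputing the total buys protection at the price of mild conservatism. It does not carry over to change from baseline, where EDF alone still leaves up to 0.076.

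The SE shortfall against total imputation also flatters the concern, because small-sample multiple imputation overstates the true SD somewhat (1.03–1.13 for joint draws in Simulation B). The comparison with the true SD is the fairer one.

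Four missing per arm is a stress case. Protocol 4.4 keeps patients who stop drug in follow-up, Protocol 6.23 asks for a biopsy at early withdrawal, SAP 3.1.2 and 3.1.8 allow wide windows, and the ITT definition drops ongoing patients who have not reached Week 26. Against this, dropouts are not replaced (Protocol 4.1), and SAP 3.1.8 foresees sites where biopsy is not allowed.

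The simulations also skip the normality rule that precedes the ANCOVA. The chronicity figures are only indicative, because the SAP imputes two of its four lesions by logistic models. Finally, the appendix listing may be abbreviated (one STDERR statement names no variable), so EDF= may be intended. That is a reason to state it.

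**Conclusion.** Both points hold and should be fixed. The separate runs are specified in the SAP text as well as the code, and nothing elsewhere restores the correlation between lesions. EDF is absent from every pooling call shown.

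The size is modest for percent change and larger for change from baseline, and it grows with the number of imputed biopsies. It rests on an assumed positive residual correlation of 0.3–0.5 and 1 to 4 wholly missing biopsies per arm. At zero correlation the SE is not understated; at negative correlation it is too large. With no missing biopsy the first point disappears. Confidence in the size is medium.

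The completer analysis in SAP 5.2.4, "requiring subjects in ITT to have valid C3G Histologic Index for disease activity scores at Baseline and Week 26", is free of both problems. None of these figures apply if van Elteren's test is used.

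**What to change.** 1. Add EDF equal to the complete-data residual df to each PROC MIANALYZE call that pools ANCOVA results: N − 3, about 41 at 44 patients and lower if the ITT set is smaller. Say so in the text of 5.2.1.
2. When the whole Week 26 biopsy is missing, impute the total activity index directly from baseline total, disease type and transplant status, by arm. State how imputed totals outside 0–21 are handled, as the appendix already does for percentages outside 0–100.
3. When only some lesions are missing, use the observed lesions of that biopsy as predictors, with a stated reduced model if it does not converge.
4. Keep lesion-level imputation for the component tables in 5.2.5, which "will also be summarized over time based on actual and imputed data".
5. Do the same for chronicity in 5.3.3.
6. Report the number of imputed biopsies by arm beside the completer result.

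The cost is SAP text, one option per pooling call and one extra imputation model per index. Intervals become slightly wider and the test mildly conservative, with size down to about 0.035 at four missing per arm. If very few biopsies are missing, item 1 does most of the work for percent change.
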